5.3 Dose Modifications

This study does not include any planned dose modifications. From Visit 3 to Visit 8, subjects will daily take the IMP orally at the assigned dose level unless discontinuation criteria as defined in Section 4.3 are met.

5.4 Measuring Subject Compliance

All treatments on visit days will be administered in the, Clinical Research Unit. Compliance for oral capsules (Visit 3 to Visit 8) will be assessed through a count of unused study medication during clinic.

5.5 Drug Accountability

In accordance with current GCP, the Investigational Site will account for all IMP supplies. Details of receipt, storage, administration, and return or destruction will be recorded in the Investigational Drug accountability record according to the SOP of the Investigational Site. Copies of the Investigational Drug accountability record will be provided to the Sponsor.

IMP will only be dispensed to subjects enrolled in this protocol, and only as directed by this protocol. Administration of IMP will be accurately recorded in each subject's source documents and CRF. Study participants will be dispensed sufficient quantities of study treatment to last until the next nominal clinic visit. Study participants will be asked to return all unused study medication for accountability at each clinic visit. Compliance with study medication is monitored and recorded by site personnel by counting the remaining study medication.

At the conclusion of the study, study drug supplies (including partially used packages) will be returned or destroyed according to instructions provided by Oramed Ltd. Drug destruction procedures and documentation must be retained at the site.

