Subjects will then undergo a treatment phase consisting of a treatment period of 12 weeks that will start at Visit 3 (Week 0) and outpatient visits at Weeks 1, 2, 4, 8, and 12 (final visit). At each visit, concomitant medication will be reviewed, weight will be measured, ORMD-0801 morning treatment will be administered in clinic, and sufficient quantity of medication will be dispensed to last until the next nominal clinic visit. Medication compliance check will be performed, self-monitored fasting morning blood glucose (finger-stick) will be recorded 3 days weekly in the morning and subjects' diaries will be reviewed. Vital signs (SBP/DBP, heart rate and oral temperature) will be recorded. Adverse events will be monitored and recorded.

At Visit 3, urine and serum pregnancy test will be performed for females of childbearing potential. Additional urine serum pregnancy test will be performed for females of childbearing potential at visits 6, 7 and 8. At Visit 8, subjects will have HbA1c evaluations and MRI-PDFF performed. At Visits 3 and 8, a complete physical exam and fibroscan will be performed.

The end of the study (EOS) Visit (Visit 9) will be conducted 4 weeks following the last scheduled treatment visit. Subjects concomitant medications will be reviewed, and weight will be measured. A complete physical exam and ECG will be performed and vital signs (SBP/DBP, heart rate and oral temperature) will be measured if deemed necessary by the investigator. Clinical laboratory evaluation will be performed. Fasting blood glucose, fasting insulin, HbA1c,

blood lipids and adiponectin levels will be measured. Urine serum pregnancy test will be performed for females of childbearing potential. Subject diaries will be collected and reviewed for self-monitored fasting morning blood glucose. Adverse events will be monitored and recorded. Subjects who are discontinued early from the study will complete the EOS evaluations at the time of early discontinuation.

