3.4 Treatment Phase (week 0)

The Treatment Phase will consist of a treatment period of 12 weeks that will start at Visit 3 (week 0) and outpatient Visits 3 (baseline) and visits at week 1, 2, 4, 8, and 12 (final visit).

At each visit patients will have:

- Concomitant medication
- Weight
- Morning treatment administration of oral ORMD-0801 insulin formulation
- Medication Compliance check.
- Urine pregnancy test at visit 3 prior to active dosing and at visits 6, 7, 8 and 9.
- Serum pregnancy test at visit 3 prior to active dosing

- Vital signs (blood pressure, heart rate, oral temperature). Vital signs will be measured in the sitting position after at least 5 minutes of rest.
- Self-monitored fasting morning blood glucose (finger-stick) of fasting blood
- AEs/SAEs assessment

3.4.1 Visits 3 (baseline), 6, 7, and 8

- At Visits 3 (baseline), 6, 7, and 8, patients will have:
- Clinical laboratory evaluations (chemistry, hematology)
- Fasting blood glucose and insulin (also used for HOMA estimates)¹
- Adiponectin
- Blood lipids: Total cholesterol, LDL, HDL, Triglycerides

3.4.2 Visits 3 (baseline), 5, 6, 7, and 8

- Return capsules - check compliance
- At visit 3 and 5 - Dispense 1 bottle of ORMD-0801
- At visits 6 and 7 – dispense 2 bottles of ORMD-0801
- Patients will take 2 capsules daily of ORMD-0801 in the morning, 30 to 45 minutes prior to breakfast and no later than 10 AM for 12 weeks.

3.4.3 Visits 3 and 8

At Visits 3 and 8 patients will have:

- Complete PE
- Fibroscan

3.4.4 Visit 8

At visit 8 Patients will have:

- HbA1C
- MRI-PDFF

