3.8 Schedule of Events

Table 1 below describes the daily schedule of events from Screening Visit 1 through End of the Study Visit 9.

Table 1: Daily Schedule of Events from Screening Through Visit 9

Assessments	Screening	Placebo	Treatment				Un Scheduled Visit	End-of-Study / Early Termination
Week	up to -6	-2	0	1	2	4	8	12
Days	Up to -42	-14	0 [±] 4	7 [±] 4	14 [±] 4	28 [±] 4	56 [±] 4	84 [±] 4
Visit	1	2	3	4	5	6	7	8
Written informed consent	X						Un Scheduled	9
Collection of Demographics	X							
Inclusion/ Exclusion	X							
Medical history	X							
Concomitant medication	X	X	X	X	X	X		X
Complete physical examination	X		X				X	(X ¹)
Height and weight and BMI	X							
Weight		X	X	X	X	X		X
Urine pregnancy	X	X	X		X	X		X
Serum pregnancy								
FSH ³	X							
Morning treatment in clinic		X	X	X	X	X	X	X

Medication dispensing		X	X	X	X	X	X	
Medication compliance check			X	X	X	X	X	
ECG	X							(X ¹)
Vital signs ⁴	X	X	X	X	X	X	X	(X ¹)
Clinical laboratory evaluations ⁵	X		X		X	X	X	X
Fasting blood glucose and fasting Insulin ⁶		X	X		X	X	X	(X ¹)
Self-monitored fasting morning blood glucose ⁷		X	X	X	X	X	X	
Adiponectin			X		X	X	X	X
HbA1C	X				X	X	X	X
Blood lipids: Total cholesterol, LDL, HDL, Triglycerides				X	X	X	X	
Fibroscan Test	X		X			X		
MRI PDFF	X					X		
Viral serology ⁸	X							
TSH	X							
AE/SAE assessment ⁹	X	X						

¹Only if investigator deems necessary

²Blood samples taken prior to dosing in clinic and snack provided after 30-45 minutes at V2, 3, 6, 7, and 8³Vital signs (blood pressure, heart rate, oral temperature). Vital signs will be measured in the sitting position after at least 5 minutes of rest.

³For females of non-childbearing potential, FSH levels will be tested if results are not available

⁴Vital signs (blood pressure, heart rate, oral temperature). Vital signs will be measured in the sitting position after at least 5 minutes of rest.

⁵Chemistry and hematology: electrolytes, Blood Urea Nitrogen (BUN), international normalized ratio (INR), creatinine, glucose, bilirubin, Liver Function Tests (LFTs) and Complete Blood Count (CBC)

⁶Fasting blood glucose and insulin will be used to determine Homeostasis Model Assessment (HOMA) estimates.

⁷Self-monitoring (finger-stick) of fasting blood glucose will required 3 days weekly in the morning, before breakfast, and recorded in patient diaries.

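### Drug supply is tied to the nominal visit date, visits may move by 4 days, and the dosing period is stated in two ways, so a drug-free gap before a late Visit 8 is possible and may go unflagged

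*Combined protocol and SAP*

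**What the plan says.** - **Supply.** Section 3.1 says that "sufficient quantity of medication will be dispensed to last until the next nominal clinic visit", and Section 5.5 repeats the rule: "Study participants will be dispensed sufficient quantities of study treatment to last until the next nominal clinic visit". Section 3.4.2 fixes the supply in whole bottles: "At visit 3 and 5 - Dispense 1 bottle of ORMD-0801" and "At visits 6 and 7 – dispense 2 bottles of ORMD-0801". It lists no dispensing at Visit 4, although Section 3.1 describes dispensing at each treatment visit. The number of capsules per bottle is left to the label (Section 5.1.1).
- **Returns.** Section 5.5 asks for all unused drug back at each visit. It does not say whether returned capsules are given out again.
- **Visit timing.** Table 1 ("Daily Schedule of Events from Screening Through Visit 9", Section 3.8) puts Visits 3 to 8 at Days 0, 7, 14, 28, 56 and 84, each with a window of 4 days either side.
- **Dosing period.** Section 5.3: "From Visit 3 to Visit 8, subjects will daily take the IMP orally at the assigned dose level". Section 3.4.2 instead gives 2 capsules a day for 12 weeks, which is 84 days.
- **Compliance.** Section 5.4 says that compliance "will be assessed through a count of unused study medication during clinic". Section 8.1.1 sets the Per Protocol band at 80% to 120%. Neither section gives a denominator.
- **What Visit 8 carries.** It has the only post-baseline MRI-PDFF and FibroScan (Sections 3.4.3 and 3.4.4). It also has fasting glucose and insulin, and the laboratory values that end the shift tables (Section 8.2.2). Section 5.2.1 has blood taken before the in-clinic dose.

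**The concern.** If the quantity handed out reaches only the nominal date, a patient who attends late but within the window has run out of capsules. The days without drug then fall directly before the visit that supplies the end-of-treatment readings for both liver fat and laboratory safety. The in-clinic dose at Visit 8 does not help the blood tests, because blood is drawn first.

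The values would still be reported as on-treatment. A patient who has used every capsule returns none, so a bare count of unused capsules looks perfect. The study is single-arm with at most 40 patients, so there is no concurrent group against which the effect of a gap could be separated from the effect of the drug. Fasting glucose and insulin are the measures most likely to respond to a few days off drug.

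**Working it through.** **Inputs.** Nominal days and windows are from Table 1. Bottle counts and 2 capsules a day are from Section 3.4.2. The compliance band is from Section 8.1.1. Day 0 is taken as the actual Visit 3. Capsules per bottle, c, is not stated. One bottle per 14 days at 2 a day implies at least 28, so 28 to 36 is examined as an assumption.

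**1. The plan's own figure.** The dispensing intervals are 14 + 14 + 28 + 28 = 84 days = 12 weeks. Bottles are 1 + 1 + 2 + 2 = 6, and 84/6 = 14 days each. The bottle schedule matches the nominal calendar exactly. No allowance for the window is stated.

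**2. Literal supply rule.** A patient seen at Visit 7 on Day 52 must be supplied to nominal Day 84: 84 − 52 = 32 days, or 64 capsules. If Visit 8 is on Day 88, the gap is 88 − 84 = 4 days. If Visit 7 is on time, the supply is 28 days against an interval of 88 − 56 = 32 days, and the gap is again 4 days.

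**3. Two bottles of fixed size, no re-issue.** The longest permitted interval from Visit 7 to Visit 8 is (84 + 4) − (56 − 4) = 36 days. Two bottles last 2c/2 = c days, so the gap is max(0, 36 − c), or max(0, 32 − c) if Visit 7 is on time.

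| Capsules per bottle (assumed) | Gap, Visit 7 on Day 52 | Gap, Visit 7 on Day 56 |
|---|---|---|
| 28 | 8 days | 4 days |
| 30 | 6 days | 2 days |
| 32 | 4 days | 0 |
| 34 | 2 days | 0 |
| 36 | 0 | 0 |

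At c = 28 the 36-day interval needs 72 capsules against 56 supplied, a shortfall of 16. Missed daily doses number 8 if the Visit 7 clinic dose comes from those bottles. They number 7 if it comes from other stock (35 home days less 28 home doses).

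**4. Returned capsules re-issued.** At c = 28 the six bottles hold 168 capsules, which is 84 days. Over all visit patterns inside the windows, the largest gap before Visit 8 is then 4 days.

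**5. Compliance in the 8-day case, all capsules taken.**

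- Capsules dispensed as denominator: 56/56 = 100%.
- Days elapsed, that interval only: 28/36 = 77.8%.
- Days elapsed, whole period: 52 dosed days before Visit 7 plus 28 after gives 80/88 = 90.9%.

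In the 4-day case the whole-period figure is 84/88 = 95.5%. Both whole-period figures lie inside 80–120%.

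**The case against.** The strongest reply is that the sections can be made to agree. The supply rule asks for a sufficient quantity, which is a floor and not a cap. Bottle size is undisclosed, so overage cannot be excluded, and re-issue of returned capsules is not forbidden. The upper Per Protocol limit of 120% fits poorly with a supply held to the exact nominal amount. A patient who stops on Day 84 and is seen on Day 88 has also completed the 12 weeks in Section 3.4.2. Section 5.5 further requires drug administration to be recorded in source documents and the CRF, so visit dates together with capsules supplied and returned could reveal a shortfall. Finally, the study is exploratory and descriptive, and nothing in it shows that a few days off drug would change MRI-PDFF or FibroScan after 12 weeks.

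Most of this stands, and it limits the point. A reader might infer that drug is supplied only to the nominal date, that an 8-day gap is built in, and that such a patient would be scored fully compliant. The documents support none of these outright. Eight days conflicts with the literal supply rule, which would carry a Day 52 patient to Day 84. It also needs an exact 28-capsule fill and no re-issue. Full compliance follows only if the denominator is capsules dispensed.

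The reply does not remove the conflict itself. The supply rule, followed as written, stops at the nominal date, whereas Section 5.3 runs dosing to the actual visit. No section says what happens between Day 84 and a late Visit 8. The diary described in Section 3.7 captures glucose values. No home-dosing entry is specified, and no date of last dose before Visit 8 is required.

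**Conclusion.** The point holds as an unreconciled conflict between the supply rule, the visit windows and two statements of the dosing period. On the literal rule, the exposure is up to 4 days without drug before a permitted late Visit 8. Across the readings the text allows, it runs from 0 to 8 days. The upper end rests on Visit 7 being 4 days early, Visit 8 being 4 days late, exactly 28 capsules per bottle and no re-issue.

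The gap may go unflagged, because the whole-period figure stays inside the Per Protocol band even in the 8-day case and the compliance denominator is undefined. It would not be invisible: days-elapsed compliance for that interval falls below 80%.

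The documents do not show a material effect on MRI-PDFF, and it may be small, so a reader should not infer that the liver-fat result is biased. The concern is greater for the pre-dose glucose, insulin and laboratory values. This should be corrected, but it does not put the study's conclusions in doubt. Confidence is medium because bottle size is unknown.

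**What to change.** - **Reconcile** Sections 3.1, 3.4.2, 5.3 and 5.5 with the Table 1 windows. The sponsor should confirm which dosing period applies and make the dispensed quantity match it, counted from the actual dispensing date. If dosing is confirmed to run to Visit 8, the quantity needs to include the permitted window. This point takes no position on which period is right and leaves the daily dose untouched.
- **State** the number of capsules per bottle, any overage, whether returned capsules are re-issued, and whether drug is dispensed at Visit 4.
- **Define compliance** in Sections 5.4 and 8.1.1 as capsules taken (dispensed less returned) over capsules due for the days elapsed, by interval and overall.
- **Record** on the CRF the date of the last dose before Visit 8, and flag Visit 8 values taken after a gap.

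The cost is one CRF field, some wording and a little more accountability work. If the window is to be covered, it also takes at most 72 − 56 = 16 more capsules per patient in a four-week interval, relative to a 28-capsule fill. If bottles already hold enough, one sentence settles the supply part.

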5.6 Concomitant Medications and Supplements

All prior medications and supplements taken within 30 days prior to the first dose of IMP and concomitant medications and supplements will be recorded in the subject's source documentation and in the CRF.

Any concomitant medication use will be evaluated on a case-by-case basis by the Investigator. If a subject requires the use of any medications, the Investigator will contact the Sponsor and the Medical Monitor to discuss the subject's continued participation in the study. In the event of an emergency, subjects will be treated at the discretion of the Investigator according to acceptable community standards of medical care.

5.7 Behavioral Restrictions

Subjects should arrive following a minimum 10-hour fast and must not take any food prior to scheduled dosing as described in the study design. Water intake will be unrestricted. All subjects will continue with their regular diet.

Excessive caffeine use (i.e., more than five cups of caffeinated beverages per day) will not be allowed from Screening through Visit 8. Excessive alcohol use or binge drinking will be discouraged during the study, and alcohol will be prohibited 72 hours prior to each visit. Subjects must refrain from tobacco or nicotine use throughout the study. Subject should not use any recreational or illicit drugs throughout the study.

Subjects will also be asked to refrain from any unusual or unaccustomed vigorous exercise during the course of the study.

6 STUDY PROCEDURES AND ASSESSMENTS

6.1 Informed Consent

According to the ICH guideline for GCP (E6) and all institutional local and state laws, the Investigator will obtain and document informed consent for each subject screened for this study. All subjects will be informed in writing of the nature of the protocol and Investigational Drug, its possible hazards, and their right to withdraw at any time, and will voluntarily sign a form (ICF) indicating their consent to participate in the study prior to the initiation of study procedures. The subject's medical record should contain written documentation indicating that informed consent was obtained. The ICF must be reviewed and approved by the Investigator's designated IRB and by Oramed Ltd. designee prior to its use. Refer to Section 11.1.4 for further details regarding informed consent.

6.2 Demographics, Medical History and Prior Medications

At Screening, demographics (sex, age, race and ethnicity), a complete medical history and social history, including smoking, caffeine, alcohol, and drug use, will be collected by subject interview. Medications and supplements, recent blood donations, illnesses, and participation in other Investigational Drug trials or clinical trials will also be recorded.

6.3 Study endpoints

The primary endpoint of this trial will evaluate safety of ORMD-0801 in patients with nonalcoholic steatohepatitis (NASH) and type 2 DM.

Secondary endpoints will evaluate the effectiveness of ORMD-0801 in reducing liver fat content in patients with NASH and type 2 DM by measuring the final and baseline differences in the MRI as liver function tests.

6.4 Efficacy Assessments

Fat content in the liver will be assessed by measuring the final and baseline differences in the MRI and Fibroscan results.

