3 INVESTIGATIONAL PLAN

3.1 Overall Study Design and Plan

This is an open, multi-center study using the oral ORMD-0801 insulin formulation in patients with NASH and confirmed type 2 DM. This exploratory multi-center study will enroll 40 patients with NASH and type 2 DM between the ages of 18 and 70. Subjects will undergo a screening phase up to 42 days prior to enrolment for 2 weeks, a treatment phase for 12 weeks and an end-of-study phase after completion of 4 weeks, after end of treatment.

At screening (Visit 1, up to week -6), subjects will sign the ICF and inclusion and exclusion criteria will be reviewed. Medical history, demographics (sex, age, race and ethnicity), and prior and concomitant medications will be recorded. Height and weight will be measured, and BMI will be calculated. Vital signs (SBP/DBP, heart rate and oral temperature), complete physical examination, 12-Lead ECG, clinical laboratory evaluations, urine pregnancy test for females of childbearing potential, blood lipids test, HbA1c, viral serology, CAP-Fibroscan and MRI-PDFF will be performed. For females of non-childbearing potential, FSH levels will be tested if results are not available. Adverse events will be monitored and recorded.

After Screening, each subject will undergo a placebo run-in phase (Visit 2, to Week -2). Concomitant medications will be reviewed. All subjects will receive the morning treatment (run in placebo) in clinic, 1 bottle of placebo medication and subject diaries will be dispensed. Vital signs (SBP/DBP, heart rate and oral temperature) and weight will be collected. Fasting blood glucose and fasting insulin will be measured, urine pregnancy test will be performed for females of childbearing potential. Self-monitored fasting morning blood glucose (finger-stick) will be recorded in the patient diaries 3 days weekly in the morning. Adverse events will be monitored and recorded.

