3.2.1 Screen Failure

A screen failure is defined as a subject who has signed the ICF, does not meet all the entry criteria outlined in Section 4 of this protocol. Note that this includes assessments through Visit 1 (up to Days -42), prior to receiving IMP.

The Investigator is responsible for keeping a record of all subjects screened for entry into the study and subsequently excluded. The reason(s) for exclusion will be recorded in the source documents and on the Screening log.

Subjects previously screen failed on eligibility criteria, may be re-screened after re-consenting at the discretion of the treating physician.

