4 STUDY SUBJECT SELECTION

4.1 Inclusion Criteria

Each subject must meet all of the following criteria to be eligible for the study:

Inclusion Criteria

1. Male or female aged 18-70 years.
2. BMI ≥ 25
3. Known type 2 DM according to American Diabetic Association (one of the three needed): Fasting Plasma Glucose ≥ 126 mg/dl or 2h postprandial (PG) following 75g OGTT ≥ 200 mg/dl or HbA1C $> 6.5-11\%$ ²⁸ or on treatment with at least one and no more than-three of the following oral anti-diabetic medications metformin, sulfonylurea, DPP-4 inhibitors, oral GLP-1 receptor agonists (semaglutide), SGLT-2 inhibitor or Thiazolidinediones (TZDs).
4. Diagnosis of NAFLD by non-invasive determination of hepatic steatosis grade S1, defined as hepatic steatosis $> 8\%$, by MRI- PDFF and CAP FibroScan ≥ 238 dB/m.
5. Liver enzyme abnormalities: ULN ≤ 5 times.
6. Fibrosis score $1 \leq F \leq 3$ as defined by FibroScan measurement (Liver stiffness measurement, LSM) of $6 \leq LSM \leq 12$ kPa.
7. Signature of the written informed consent.
8. Negative pregnancy test at study entry for females of childbearing potential.
9. Females must have a negative urine pregnancy test result at screening, prior to the start of the run-in period, at initiation of active dosing and every 4 weeks following till the end of the study. A negative urine and serum pregnancy test must be obtained prior to active dosing. Males and females of childbearing potential must use two methods of contraception, one of which must be a highly effective method from the time of screening to the last dosing study visit (22 weeks).

Highly effective methods include:

- o combined (estrogen and progestogen containing) hormonal contraception (oral, intravaginal or transdermal) associated with inhibition of ovulation
- o progestogen-only hormonal contraception (oral, injectable or implantable) associated with inhibition of ovulation
- o intrauterine device (IUD)
- o intrauterine hormone-releasing system (IUS)
- o bilateral tubal occlusion

Acceptable methods include:

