8.2.2 Laboratory Evaluations

Individual clinical safety lab (hematology, serum chemistry and serology) values will be listed by visit and summarized using descriptive statistics as appropriate (i.e., mean, median, range, and standard deviation for continuous data and frequency for categorical data). Individual change from baseline (Screening) in laboratory values will be calculated and summarized descriptively. Shift tables from baseline (Screening) to post-dose (Visit 8) will also be produced for the laboratory assessments based on the categories of Low, Normal, and High. A clinically significant change from baseline will be recorded as an AE if deemed appropriate by the Investigator.

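### The qualifying MRI is the only MRI baseline in this single-arm trial, and the FibroScan baseline is not named, so part of any fall in liver fat may be regression to the mean

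*Combined protocol and SAP*

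**What the plan says.** **Entry.** Inclusion criterion 4 (Section 4.1) requires steatosis above 8% "by MRI- PDFF and CAP FibroScan ≥ 238 dB/m". Both limits are lower cut-offs. Criterion 6 requires a fibrosis score "as defined by FibroScan measurement (Liver stiffness measurement, LSM) of" 6 to 12 kPa, which is a two-sided window.

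**Efficacy measure.** Section 6.4: "Fat content in the liver will be assessed by measuring the final and baseline differences in the MRI and Fibroscan results". Neither this section nor Section 6.3 names the baseline visit.

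**Timing of MRI.** Section 3.1 schedules it at Screening ("viral serology, CAP-Fibroscan and MRI-PDFF will be performed") and at the end of treatment ("At Visit 8, subjects will have HbA1c evaluations and MRI-PDFF performed"). No other MRI is planned.

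**Timing of FibroScan.** It is done at Screening and twice more. Section 3.4.3: "At Visits 3 and 8 patients will have" a complete physical examination and a FibroScan. Visit 3 is week 0, after the two-week placebo run-in.

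**Which visit is baseline.** The subsections of Section 3.4 label Visit 3 as baseline. The safety analysis uses Screening: "Individual change from baseline (Screening) in laboratory values will be calculated" (Section 8.2.2), and Sections 8.2.3 and 8.2.5 do the same.

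**Analysis.** The synopsis plans descriptive statistics for change from baseline and for the value at each time point. Section 8 has no efficacy subsection and refers further detail to a statistical analysis plan, for which the document supplied contains no separate text. Section 8.1 calls the study exploratory and not powered, but its size sufficient to show trends of falling liver fat.

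**Re-screening.** Under Section 3.2.1, screen failures "may be re-screened after re-consenting at the discretion of the treating physician".

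**The concern.** A reading that admits a patient because it exceeds a cut-off contains, on average, some upward measurement error and short-term variation. The next reading is expected to be lower without any treatment. When the same reading then serves as baseline, this fall enters the estimated change. A randomised control arm would cancel it; this trial has none.

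The direction matters more than usual here. The plan looks for a trend rather than a significant difference, so the sign and size of the mean change are the result. For PDFF and CAP the artefact points the way the sponsor hopes to see. It is systematic, so more patients would not shrink it.

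The trial already collects the data to remove it for FibroScan. The Visit 3 reading was not used for selection, and no active drug is scheduled between Screening and Visit 3. The plan does not say that this reading is the efficacy baseline, nor does it specify a Screening-to-Visit 3 comparison. With two candidate baselines and no rule, the choice could also be made after the data are seen.

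**Working it through.** **Inputs from the documents.** PDFF above 8%; CAP at least 238 dB/m; LSM 6 to 12 kPa; up to 40 patients; the visit schedule above. Section 8.1 gives no standard deviation, effect size or power, so there is no efficacy figure to reproduce. Its country split adds up: 20 + 10 + 10 = 40.

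**Assumed inputs.** All means, standard deviations (SD) and reliabilities below are assumptions.

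**Step 1: closed form, one cut-off at a time.** For a normal screening value with mean m, standard deviation s and test-retest reliability r, truncated below at cut-off k, the expected fall with no drug effect is

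(1 − r) × s × φ(c) / (1 − Φ(c)), with c = (k − m)/s.

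- PDFF, m = 12, s = 8, r = 0.95: c = (8 − 12)/8 = −0.5; φ/(1 − Φ) = 0.509; fall = 0.05 × 8 × 0.509 = 0.20 points.
- CAP, m = 290, s = 60, r = 0.8: c = (238 − 290)/60 = −0.867; φ/(1 − Φ) = 0.340; fall = 0.2 × 60 × 0.340 = 4.1 dB/m.
- PDFF over m = 8 to 16, s = 6 to 8, r = 0.80 to 0.98: 0.02 to 1.28 points, and at most 0.32 when r is 0.95 or more.
- CAP over m = 260 to 320, s = 45 to 60, r = 0.6 to 0.9: 0.4 to 13.9 dB/m.

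**Step 2: simulation with all three criteria applied together and no drug effect.** Each scenario has 1,000,000 screened patients. True PDFF is lognormal (median 10 or 13%, log SD 0.6). True CAP has mean 270 or 290 and between-patient SD 45 dB/m, correlated 0.6 with log PDFF. LSM is lognormal (median 6.5 kPa, log SD 0.4, 15% within-patient variation). Errors are independent between visits, and selection is on the Screening reading.

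| Measure and baseline | Within-patient SD | Mean change | Standard error, n = 40 |
|---|---|---|---|
| PDFF from Screening | 0.5 points | −0.01 to −0.03 | 0.11 |
| PDFF from Screening | 1.0 | −0.05 to −0.11 | 0.22 |
| PDFF from Screening | 1.5 | −0.12 to −0.24 | 0.33 |
| PDFF from Screening | 3.5 | −0.58 to −1.04 | 0.76 |
| CAP from Screening | 25 dB/m | −2.0 to −4.5 | about 5.5 |
| CAP from Screening | 40 dB/m | −6.2 to −11.4 | about 8.5 |
| CAP from Visit 3 | 25 or 40 dB/m | within ±0.2 | not needed |

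The CAP rows use PDFF SDs of 0.5 to 1.5. A second set of four joint scenarios, with normal distributions, gave −0.03 to −0.74 points for PDFF, −0.2 to −9.4 dB/m for CAP from Screening, and −0.17 to +0.01 dB/m for CAP from Visit 3. The smallest values came from patients screened well above the cut-offs with highly reliable readings.

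**Step 3: effect on the sign of the result.** With an inert drug and no bias, the observed mean falls with probability 0.50. With bias b it is about Φ(b/SE). For PDFF: Φ(0.02/0.11) = 0.57 at SD 0.5; Φ(0.12/0.33) = 0.64 at the low end of SD 1.5; Φ(1.04/0.76) = 0.91 at the high end of SD 3.5. For CAP from Screening: Φ(2.0/5.5) = 0.64 to Φ(11.4/8.4) = 0.91.

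**Step 4: liver stiffness.** Because the window is two-sided, φ(c)/(1 − Φ(c)) becomes (φ(a) − φ(b))/(Φ(b) − Φ(a)), with a = (6 − m)/s and b = (12 − m)/s. With s = 3 and r = 0.8, m = 6 gives 0.2 × 3 × 0.723 = a fall of 0.43 kPa; m = 9 gives zero; m = 12 gives a rise of 0.43 kPa. The direction is not fixed.

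**The case against.** Four readings go further than the documents allow.

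- A reader might infer that the screening FibroScan is the efficacy baseline. The documents do not say so. The Screening definition appears only under the Section 8.2 heading on safety evaluation, while Section 3.4 labels Visit 3 as baseline and pairs the Visit 3 and Visit 8 FibroScans. On that reading the CAP bias is about zero.
- A reader might infer that liver fat will appear to fall. That is too certain. If MRI is highly repeatable the PDFF bias is negligible, and in most scenarios the bias is no larger than about one standard error at n = 40.
- A reader might add liver stiffness to the case. It measures stiffness rather than fat, and Step 4 shows that its bias can go either way.
- A reader might say that the Visit 3 FibroScan is ignored. The synopsis plans values at each time point, so it would be tabulated. What is missing is the named baseline and the comparison.

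Re-screening could add to selection, because no limit on attempts is stated. Repeating a measurement until it passes is not described, and no size is claimed for it here.

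It is also fair that efficacy is secondary and descriptive in an exploratory safety study. That lowers the stakes but does not remove them, since a descriptive mean change is exactly what this bias distorts.

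Two technical cautions stand. Section 5.2.1 places blood samples and weights before dosing but does not mention FibroScan, so the Visit 3 scan is only presumably pre-dose. And the near-zero bias from Visit 3 assumes independent errors; if CAP drifts slowly over weeks, some selection effect persists at Visit 3.

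**Conclusion.** The concern holds in a limited form. For MRI-PDFF, the qualifying scan is the only possible baseline under any reading, so some favourable regression to the mean is expected: about 0.01 to 1.0 percentage points under the main assumed inputs, and small if repeatability is good. For CAP, the plan leaves the baseline open between two visits that behave very differently with no drug effect: a fall of about 2 to 11 dB/m from Screening under the main inputs (as little as 0.2 and as much as 13.9 under the others tried), against about zero from Visit 3. No directional claim is made for stiffness.

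The direction for PDFF and CAP follows from the lower cut-offs and the single arm. The sizes rest entirely on assumed distributions, because the documents give none. The change is worth making because it is nearly free and settles the baseline before the data are seen.

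**What to change.** In Section 6.4 and the statistical analysis plan:

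1. Define the efficacy baseline for CAP and LSM as the Visit 3 FibroScan, and state that it is performed before the first active dose.
2. Tabulate the Screening-to-Visit 3 change (no active drug) beside the Visit 3-to-Visit 8 change in the same patients. Note that the intervals differ: up to 6 weeks, including the two-week placebo run-in, against 12 weeks.
3. Keep Screening as the MRI-PDFF baseline, and state that the change from it includes regression to the mean of unknown size.

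Two additions that may suggest themselves are not worth making. A sensitivity summary using the first qualifying scan of re-screened patients would reuse the very value that passed the cut-off. Splitting at most 40 patients by distance from 8% would leave groups too small to read.

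The cost is a few sentences and one table, with no new visit or scan. The sponsor's downside is a probably smaller reported CAP change than one measured from Screening.
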